If the subject is unable to consent (incompetent, impaired decision-making capacity), the subject's legally authorized representative will be asked to provide verbal informed consent, and the subject's Personal Representative will be asked to provide written HIPAA authorization. No subjects who are unable to consent will be enrolled in the study unless verbal consent has been obtained from a legally authorized representative and written HIPAA authorization has been obtained from a Personal Representative. Local research personnel will follow all applicable laws and regulations. VHA Directive 1605.01 defines a personal representative as a person who, under applicable law, has authority to act on behalf of the individual to include privacy- related matters. The authority may include a power of attorney, legal guardianship of the individual, appointment as executor of the estate of a deceased individual, or a Federal, State, local or tribal law that establishes such authority (e.g., parent of a minor)." Competency of the subject will be determined by previous clinical assessment as documented in the medical record. If competency has not been documented in prior notes and we determine that the subject cannot consent, then discussion with the treating team regarding capacity to consent will ensue. In case of patients deemed incompetent or with impaired decision-making capacity, the legal representative would be contacted first and then a relative asked to consent for them. The legally authorized representative for the subject will be documented in the medical record (progress note or copy of legally recognized document). If the subject is later deemed to be competent, they will be re-consented as soon as possible. The plan for re-consenting subjects with fluctuating decision-making capacity or those who regain consent capacity is to review the study and consent materials and provide information on their previous participation and surrogate consent. Subject dissent would overrule surrogate consent. The subject or their representative (legally authorized representative or Personal Representative) will be first approached by the clinical care team to assess their interest in the trial. The following persons will be contacted in the following order of priority: a. health care agent (individual named as a power of attorney), b. legal guardian or c. next of kin in this order (spouse, child, parent, sibling, grandparent or grandchild) or d. close friend. The subject's medical record will be examined to determine whether a Personal Representative is documented. If a Personal Representative is not identified from the medical record, research personnel will ask the legally authorized representative whether the subject has a Personal Representative, and if so, who the Personal Representative is. The Personal Representative will be provided with the study information sheet and HIPAA authorization form. If the subject's legally authorized representative is also a subject's Personal Representative, they will be asked to provide both verbal consent and written HIPAA authorization. If no Personal Representative is identified, or the Personal Representative does not provide written HIPAA authorization, the subject will not be enrolled in the study unless they later gain capacity to

provide consent and HIPAA authorization for themselves, even if a separate legally authorized representative has provided verbal consent for the subject's participation.

Documentation by a qualified practitioner in the individual's medical record in a signed and dated progress note that the individual lacks capacity to make the decision to participate in the proposed study. NOTE: the qualified practitioner may be a member of the research team OR the individual has been ruled incompetent by a court of law. Disclosures required by the VA to be made to the subject by the investigator (the informed consent process) must be made to the subject's surrogate(s) (legally authorized representative and Personal Representative).

Discussion of the major aspects of the study with the surrogate(s) may take place either in person or over the phone. The surrogate(s) will be informed that their decision should be based upon that which the surrogate believes is, or would be, desired by the subject. If a subject's wishes cannot be determined, surrogate decisions should be based upon that which the surrogate believes to be in the subject's best interest. If feasible, the practitioner will explain the proposed research to the prospective research subject even when the surrogate gives consent. Under no circumstances will the subject be forced or coerced to participate in a research study. Local site study personnel will be required to complete VA human subject protections training requirements prior to the start of the intervention phase of the study. In addition, local research staff will attend a virtual training session on how to obtain and document informed consent that will be conducted by the coordinating site (Madison VA) research staff.

#### **INTERVENTION (UNIVERSAL GLOVING)**

As this is a cluster randomized trial, all healthcare workers/patients within a unit will need to participate in the intervention/comparator (as assigned) and data collection in order to ensure meaningful data.

If the patient lacks decision-making capacity, the research staff will provide information to the caregiver(s)/Legally Authorized Representative (LAR). The information will be given to caregiver(s)/LAR when the subject is unconscious or clearly lacking capacity. When a caregiver/ LAR is not present in the unit, the study information sheet will be mailed. The mailing will be determined in the following order of priority: a. health care agent (individual named as a power of attorney), b. legal guardian or c. next of kin in this order (spouse, child, parent, sibling, grandparent or grandchild) or d. close friend. This information will be determined by unit staff using established procedures.

#### **SURVEYS/INTERVIEWS**

Patients and healthcare workers who are participating in surveys and/or interviews/focus groups will be informed that participation is voluntary and that they may withdraw from participation at any time, without prejudice. The rights and welfare of the participants will be protected by emphasizing to them that the quality of their medical care will not be adversely affected if they decline to participate in this study. They will receive information sheets describing the purpose of the study, the procedures involved, and who to contact for further information.

#### **5.5 Inclusion/Exclusion Criteria**

VA inpatient units meeting the following criteria are eligible to participate in the study:

1. Ability to identify one of the following inpatient units as defined by CDC National Healthcare Safety Network by reviewing prior 12-month patient mix data (at least 80% of patients meet patient type):

- a. Adult Acute Medical Ward: Hospital area for the evaluation and treatment of patients with medical conditions or disorders.
- b. Adult Acute Medical/Surgical Ward: Hospital area for the evaluation of patients with medical and/or surgical conditions.
- c. Adult Acute Surgical Ward: Hospital area for evaluation and treatment of patients who have undergone a surgical procedure.
- 2. Ability to store collected admission and discharge stool samples from patients prior to batch mailing
- 3. Ability to collect and upload data (HAIs, mortality, length of stay, hand hygiene and barrier precaution compliance; glove use and glove plus gown use for CP) required for analysis
- 4. Local R&D Committee approval
- 5. Letter of support from the Hospital Director or Chief of Staff.

Intensive care units, long term care units, and mixed-acuity will be excluded. To participate

in interviews or focus groups, the individual must be:

- 1. 18 years of age or older
- 2. A patient admitted to the participating unit OR a healthcare worker who has regular work duties on the participating unit.

To participate in specimen and clinical data collection, the individual must be:

- 1. 18 years of age or older
- 2. A patient admitted to the participating unit.

## 5.6 Study Evaluations

### Patient-level data

**C. difficile Acquisition:** In both the intervention and control groups, we will obtain one swab or stool sample upon admission and one swab or stool sample upon discharge to test for the presence of *C. difficile*. This outcome data will be collected on an individual patient level, but de-identified prior to reporting. These test results will not be available to healthcare workers or patients at participating sites. Acquisition will be defined as a patient who has an initial test (via stool or perirectal swab) upon unit admission that is negative for *C. difficile* and a subsequent discharge test within the same unit that is positive for *C. difficile*.

### Specimen collection

Research staff and/or clinical staff in both the intervention and control arms of the study will implement a standard protocol for obtaining stool or perirectal swab (depending on patient preference) samples for *C. difficile* test using standardized clinical methodology. Samples will be collected within 72 hours of patient admission and within 72 hours of anticipated discharge of all patients in participating units. *C. difficile* testing via stool sample will be obtained by using a toilet hat to collect stool and storing a sample of the stool in a sterile contained. *C. difficile* testing via perirectal swab sample will be obtained by swabbing the perianal area (a swab from the anal verge, without rectal insertion) in a circular motion, ideally until visible stool is noted on swab. The swab samples will be obtained in a private room or the privacy curtain will be drawn in semi-private rooms to protect patient privacy. The discharge sample may be collected within 72 hours prior to estimated discharge date or, if the patient is transferred to another unit within the participating facility, within 48 hours after discharge from the unit. Samples collected by research staff will be labeled with unique identifier. Samples collected by clinical staff or patient self-collected samples will be labeled in the unit by clinical staff with standard clinical pre-printed patient labels and collected on site by Research Assistants who will relabel specimens with unique identifiers. These collected samples will be refrigerated according to procedures defined by laboratory staff to ensure sample quality and then ship in batches to the Madison VA research laboratory.

The specimens will be shipped to a central microbiological research laboratory at the Wm. S.

Middleton Memorial VA Hospital in accordance with mandated U.S. regulations governing the shipment of Diagnostic Samples, Dangerous Goods and dry ice. No patient identifiers will be received by the central laboratory. Microbiological work-up for *C. difficile* will follow Clinical and Laboratory Standards Institute procedures and the use of a central microbiological laboratory to process these specimens will assure standardized microbiological (or molecular) methods and processing of the samples. Specimens will be tested for *C. difficile*, and *C. difficile* isolates will be tested for *in vitro* cytotoxin production using previously described procedures. Shipments will be tracked using a shared database stored on the VA server.

Participants (patients and staff) will not be informed of the results of the cultures. The cultures are measuring *C. difficile* colonization, not infection. There is currently no treatment for *C. difficile* colonization, and many patients who are colonized with *C. difficile* are and remain asymptomatic. Thus, informing participants of a positive *C. difficile* culture could result in undue stress and unnecessary treatments to the patient given the possibility that the colonization will remain asymptomatic. In addition, it remains unknown whether altering behaviors of healthcare workers could impact the spread of *C. difficile* from asymptotically colonized patients and thus there is no standard for how to care for a patient that is found to be asymptotically colonized. So, it is not currently useful to inform healthcare workers simply of positive cultures. However, patients that develop symptoms of *C. difficile* infection, such as diarrhea, will be cultured and treated according to the standard of care in all intervention and control units. Specimen results will be stored on a database on the VA server, unless otherwise specified in a valid DUA.

**Demographics:** In both the intervention and control groups, for patients who consented to clinical data collection, we will obtain data on demographic characteristics (age, gender, race, weight, height) from VA administrative records (e.g., Corporate Data Warehouse [CDW] files). These data will be linked to patient specimen results (e.g., *C. difficile* colonization) and stored on a shared database on the VA server, unless otherwise specified in a valid DUA.

**Past medical history/other hospitalization characteristics:** In both the intervention and control groups, for patients who consented to clinical data collection, we will obtain data on the following characteristics from VA administrative records (e.g., using healthcare utilization dates, prescriptions, and diagnostic/treatment codes from CDW files): hospitalization characteristics (dates of admission to and discharge from the healthcare facility and participating unit, disposition [to acute care, home, home services, or skilled nursing facility/nursing home/long-term care facility], and source [i.e., where the patient was admitted from], treatments and healthcare utilization within the 90 days prior to admission and CDI occurring during their admission (antibiotic use, proton-pump inhibitor use, visits to healthcare facilities [emergency department, infusion services such as chemotherapy, hemodialysis]), CDI-related surgical intervention prior to admission, and comorbidities (acute renal failure, asthma, cancer, congestive heart failure, chronic obstructive pulmonary disease, cardiovascular disease, dementia, diabetes, inflammatory bowel disease, liver disease, paralysis, peripheral vascular disease, renal disease, rheumatic disease, peptic ulcer disease]). These data will be linked to patient specimen results and stored on a shared database on the VA server, unless otherwise specified in a valid DUA.

***C. difficile* infection:** In both the intervention and control groups, we will determine the development of *C. difficile* infection during admission among patients who consented to clinical data collection by obtaining data from VA administrative records (e.g., using diagnostic codes from CDW files). These data will be linked to patient specimen results and stored on a shared database on the VA server, unless otherwise specified in a valid DUA.

**Other Healthcare-Associated Infections:** The incidence of other HAIs including: 1) catheter-associated bloodstream infection (CLABSI), 2) catheter-associated urinary tract infection (CAUTI), and 3) MRSA HAIs during admission among patients who consented to clinical data collection will be obtained from VA administrative records (e.g., using diagnostic codes from CDW files) for both the intervention and control groups. These data will be linked to patient specimen results and stored on a shared database on the VA server, unless otherwise

specified in a valid DUA.

**Mortality:** In both the intervention and control groups, mortality among patients who consented to clinical data collection will be obtained from VA administrative records (e.g., using date of death from the CDW files). These data will be linked to patient specimen results and stored on a shared database on the VA server, unless otherwise specified in a valid DUA.

**Other clinical outcomes:** In both the intervention and control groups, for patients who consented to clinical data collection, whether the patient had toxic megacolon or a colectomy will be obtained from VA administrative records (e.g. using diagnostic/treatment codes from CDW files). These data will be linked to patient specimen results and stored on a shared database on the VA server, unless otherwise specified in a valid DUA.

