### **5.8 Data Analysis**

#### **5.7.1 Sample Size Determination**

Initial power calculation determined that 10 patient units are necessary to detect a 36% relative reduction (6.2%) in acquisition of *C. difficile* in the intervention vs. no reduction in the control group based on a presumed rate of 9.7 acquisitions per 1,000 patient days; recent literature report an average *C difficile* acquisition rate of 9.7 per 1,000 patient-days and expected reduction of *C. difficile* acquisition of 36%. Each arm of the study will require 9,879 patient days of care. On average, it is estimated that each patient unit will have a 25-bed capacity with an estimated 100 admissions per month and 5-day length of stay. We will plan to enroll 10 units, 5 for each arm. These power calculations will be revised based on actual baseline-period data. The statistical power calculation was conducted using G\*Power. We have incorporated an intracluster coefficient of 0.40 for this study.

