### 5.7.2 Statistical Analyses

Analyses will be conducted by the lead biostatistician in collaboration with resources from the Coordinating Site Committee (see above).

**Demographics:** All unit level and patient level categorical demographic information will be summarized on table 1 as proportions and frequencies. We will output all continuous data using mean plus standard deviation or median plus range.

**C. difficile acquisition Rate:** Acquisition rates will be obtained from each unit and comparisons for differences between control and intervention units using a chi-squared test. We will conduct a crude and adjusted linear and logistic regression model to determine predictors of C.diff acquisition in patients. Additionally, we will model the incidence of C.diff acquisition for intervention and control patients using Poisson regression models and to determine the gloving impact.

**CDI Infection Rate:** For unit-level data, we will compare changes in CDI infection rates between the intervention and control units using the chi-squares test or Fisher's exact test with post-hoc pairwise comparisons. For patient-level data, infection rates will be modelled for specific time periods (during 3, 6, 9 and 12 months; or every 3 months of the study period [up to 24 months]) using incidence split modeling to determine the point of highest infection within each unit, with appropriate covariate adjustment. We will use the Royston's trend test to conduct a time-trend analysis for CDI infection rates for specific time periods (during 3, 6, 9 and 12 months; or every 3 months of the study period).

**Other HAI Rates:** All other rates between intervention and control units will be compared using chi-squared test or Fisher's exact test, with post-hoc pairwise comparisons. All incidence and risk analysis will be conducted using Poisson regression models with covariate adjustment. For specific time periods (during 3, 6, 9 and 12 months; or every 3 months of the study period), we will use incidence split modeling to determine the point of highest infection within each unit, with appropriate covariate adjustment. We will use the Royston's trend test to conduct a time-trend analysis on the monthly HAI (CAUTI and CLABSI).

**Length of Stay:** A weighted two-sample and paired t-test will be used to compare mean length of stay between the intervention and control units.

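### Two rules decide whether a post-transfer specimen counts, and the main acquisition comparison fixes no person-time although the specimen windows overlap at the planned stay

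*Combined protocol and SAP*

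**What the plan says.** Section 5.6 (Patient-level data) calls for "one swab or stool sample upon admission and one swab or stool sample upon discharge". It counts an acquisition when the admission test is negative and there is "a subsequent discharge test within the same unit that is positive for" *C. difficile*. Under Specimen collection, the same section sets the timing: "Samples will be collected within 72 hours of patient admission and within 72 hours of anticipated discharge of all patients in participating units". That subsection also accepts a discharge specimen up to 48 hours after the patient has left the unit by transfer elsewhere in the facility. Section 5.2.1 places one intervention unit and one control unit at every site.

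Section 5.7.1 sizes the trial "based on a presumed rate of 9.7 acquisitions per 1,000 patient days", on units with "25-bed capacity with an estimated 100 admissions per month and 5-day length of stay", and concludes: "Each arm of the study will require 9,879 patient days of care".

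For the analysis, Section 5.7.2 states: "Acquisition rates will be obtained from each unit and comparisons for differences between control and intervention units using a chi-squared test". It adds linear and logistic regression for predictors, and then says that "we will model the incidence of C.diff acquisition for intervention and control patients using Poisson regression models". It names no denominator, at-risk set or offset for acquisition. Section 5.6 (Unit-level data) does give denominators for the other infections: device-days for CLABSI and CAUTI, patient-days for MRSA.

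**The concern.** There are two problems, both on the main outcome.

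First, a positive specimen taken after transfer is an acquisition under the collection rule and is not one under the definition. Two analysts following the protocol could report different event counts. Because both arms are present at each site, the receiving unit could be the opposite-arm unit.

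Second, an acquisition can be detected only between the two specimens. The planning counts whole days of care, but the listed analyses do not say what the rate is a rate of. A chi-squared test compares proportions of patients, so it takes no account of how long each patient was observed, and it ignores that units were randomised. The Poisson model could use person-time, but none is named. If stay differs between arms, the estimate moves with the denominator chosen. Unit length of stay is itself an outcome to be compared (Section 3.0), so the choice should be made before the data are seen.

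**Working it through.** **The plan's own figure.** Section 5.7.1 gives 9.7 per 1,000 and a 36% reduction: 9.7 × 0.64 = 6.2 per 1,000. Alpha and power are not stated; I assume two-sided 5% and 80%. With p₁ = 0.0097 and p₂ = 0.0062:

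n = (1.960 + 0.8416)² × [p₁(1−p₁) + p₂(1−p₂)] / (p₁−p₂)² = 7.849 × 0.015767 / 0.00001225 ≈ 10,103 per arm.

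This is 2.3% above the stated 9,879; an arcsine version gives 9,983. Other unstated choices fit too (one-sided 85% power with continuity correction gives 9,868 using the exact 36% reduction). All of these treat each day of care as a unit of observation.

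**Overlap of the windows.** Admission window: hours 0–72. Discharge window at a 120-hour stay: hours 48–120. Overlap = 144 − 120 = 24 hours. It is 48 hours at a 4-day stay, complete at 3 days or less, and zero from 6 days upward.

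**Effect of the denominator, one case by hand.** Assumptions: no true effect, a hazard of 0.0097 per day in both arms, a fixed 5-day stay, specimens taken on average 1 day from each end (uniform within 48 hours), and stays 10% shorter in one arm.

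- Gap between specimens: 5 − 2 = 3 days against 4.5 − 2 = 2.5 days.
- Risk per patient: 1 − exp(−0.0097 × 3) = 0.02868 against 1 − exp(−0.0097 × 2.5) = 0.02396.
- Ratio per patient: 0.02396 / 0.02868 = 0.84. Per care-day: (0.02396/4.5) / (0.02868/5) = 0.93. Per specimen-to-specimen day: (0.02396/2.5) / (0.02868/3) = 1.00.
- If 1% of admission-negatives are missed carriers, the risks become 0.01 + 0.99 × 0.02868 = 0.03839 and 0.01 + 0.99 × 0.02396 = 0.03372. The ratios are then 0.88, 0.98 and 1.05.

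**Range by simulation** (3,000,000 stays per case before the two-day limit). Specimens were uniform within 24, 48 or 72 hours of each end. Stays were fixed at 5 days, or exponential, gamma (shape 2) or lognormal (CV 1), limited to 2 days or more with mean 5.0. Reversed pairs were dropped. Every stay in one arm was multiplied by 0.90, with no true effect.

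| Missed carriers (assumed) | Per patient | Per care-day | Per specimen-to-specimen day |
|---|---|---|---|
| none | 0.84–0.89 | 0.93–0.98 | 1.00 |
| 1% | 0.88–0.92 | 0.98–1.00 | 1.03–1.07 |
| 2% | 0.90–0.93 | 1.00–1.02 | 1.05–1.10 |

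Missed carriers work against the specimen-to-specimen offset because they do not scale with the gap: shorter gaps carry the same false events over less time.

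**Apparent rate per 1,000 care-days, equal stays.** If 9.7 is a true hazard and no carriers are missed, the rate is 7.5–7.6, 5.7–6.0 or 4.1–5.2 for sampling within 24, 48 or 72 hours. With 1% missed carriers the overall range is 6.1–9.5.

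**Post-transfer specimens.** Assumptions: true ratio 0.64, 5-day stay, a share f sampled on average 1 day after leaving, and intervention patients moving to standard care.

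- Mildest case (24-hour sampling): untransferred patients have a 4-day gap; transferred patients have 4.5 days in the unit plus 1 after. Controls move to standard care. At f = 10%: (0.9 × 4 × 0.64 + 0.1 × (4.5 × 0.64 + 1)) / (0.9 × 4 + 0.1 × 5.5) = 2.692 / 4.150 = 0.649.
- Strongest case (72-hour sampling): gaps of 2.14 days, and 3.5 days plus 1. Controls move to a gloving unit. At f = 10%: (0.9 × 2.14 × 0.64 + 0.1 × (3.5 × 0.64 + 1)) / (0.9 × 2.14 + 0.1 × (3.5 + 0.64)) = 1.557 / 2.340 = 0.665.

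At f = 5% the range is 0.64–0.65, and at 30% it is 0.66–0.71.

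**The case against.** **The denominator is implied.** Section 5.7.1 plans in patient-days, unit admission and discharge dates are collected, and the definition of acquisition points to admission-negative patients with a discharge test. Patient-days is therefore the natural reading of the Poisson model. This stands, and a missing offset alone would be a matter of detail. It does not rescue the chi-squared test, which cannot use person-time or the randomised unit. Section 5.7.2 does not label that test primary, but it lists it first and does not say which analysis decides.

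**The windows are outer limits.** The definition asks for specimens at admission and discharge, and a later second test. Actual timing may be tighter, and the order of the tests is protected. This stands; it is why 24 and 48 hours are shown as well. No minimum gap is set, however.

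**The post-transfer conflict is verbal.** The same-unit phrase could mean the same unit stay, with the specific collection rule governing. That reading is possible, but the text does not say it, and one sentence would settle it.

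**Collection times may be recorded anyway.** Section 4.2 refers to separate collection guidelines that are not shown. Silence here does not show that times will be lost.

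**Conclusion.** The plan gives two classifications for the same post-transfer specimen, and its first-listed acquisition comparison uses neither person-time nor the unit of randomisation. Both should be settled before analysis.

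The size is conditional. At 5–10% post-transfer sampling, a true 0.64 moves only to 0.64–0.67, so the conflict matters little unless transfers are common. The tabulated ratios need a 10% difference in stay, which is assumed.

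A reader might infer three stronger things that the documents do not support:

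- *That the overlap biases the comparison.* With equal stay and specimen timing in both arms it does not, and no document says that gloving changes stay.
- *That specimen-to-specimen days are the one correct denominator.* They are unbiased here only if the admission test misses essentially no carriers. At 1–2% missed, care-days stay closer to 1 (0.98–1.02 against 1.03–1.10). Neither is free of bias.
- *That the observed rate must fall short of 9.7.* That requires 9.7 to be a true hazard, and how the cited rate was measured is not shown. If it came from paired specimens per patient-day, no shortfall need arise.

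**What to change.** 1. Reconcile the acquisition definition with the collection rule in Section 5.6 so that one rule governs specimens taken after transfer. Report results with and without them.
2. In Section 5.7.2, make the main acquisition comparison a cluster-aware Poisson (or equivalent) rate model among admission-negative patients with a discharge specimen, in place of the chi-squared test. Fix the person-time offset before the data are seen: either those patients' unit patient-days, which matches Section 5.7.1, or specimen-to-specimen days. Use the other as a sensitivity analysis.
3. Keep the collection date and time of both specimens, report the gap between them by arm, and state the person-time in Section 5.7.1 in the same units as the chosen offset.

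The cost is revised wording in the endpoint and analysis sections, a little more analysis work, and two collection times kept per patient in the dataset.

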**30-Day Mortality:** Using patient level data, we will conduct a 30-day survival analysis to determine the hazard of mortality for control and intervention units using a cox proportional hazards model with Kaplan Meier curves. Within each unit, a risk analysis will be conducted to

determine the predictors of 30-day mortality. Additionally, we will examine survival percentages at specific periods of the intervention period (i.e. 3, 6, 9 and 12 months; or every 3 months of the intervention period) using life tables and log-rank tests to determine at which points mortality was highest for each unit.

*Other clinical outcomes:* Rates of toxic megacolon and colectomy will be compared between intervention and control units using chi-squared test or Fisher's exact test, with post-hoc pairwise comparisons. All incidence and risk analysis will be conducted using Poisson regression models with covariate adjustment. For specific time periods (during 3, 6, 9 and 12 months), we will use incidence split model to determine the point of highest infection within each unit, with appropriate covariate adjustment. We will use the Royston's trend test to conduct a time-trend analysis on the monthly outcomes.

*Intervention Fidelity:* We will calculate the compliance rates for both the intervention and control units and compare them using a chi-squared test. We will conduct a univariate logistical regression model to determine the odds of compliance with respect to additional unit characteristics such as number of beds and location. Monthly compliance will be modeled using a time series graphing technique with trend analysis estimates.

*Isolation Days of Care:* Monthly aggregate data of isolation patients will be collected from infection control at participating sites which are collected as standard of care and we will estimate the days of care by multiplying this number by the average length of stay for the participating unit. We will make comparisons between the intervention and control groups using the analysis of variance (ANOVA).

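### Colectomy and toxic megacolon have no stated CDI link and no time window from unit admission, so colectomies done for other reasons can be counted and compared between arms.

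*Combined protocol and SAP*

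**What the plan says.** **Definition.** Section 5.6, patient-level data, Other clinical outcomes: for patients who consented to clinical data collection, "whether the patient had toxic megacolon or a colectomy will be obtained from VA administrative records". The source is given as an example, "using diagnostic/treatment codes from CDW files", with no code list. The only linkage stated is "These data will be linked to patient specimen results and stored on a shared database on the VA server".

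**Analysis.** Section 5.7.2, Other clinical outcomes: "Rates of toxic megacolon and colectomy will be compared between intervention and control units using chi-squared test" or Fisher's exact test. Poisson models with unnamed covariates, analyses by period and a trend test on monthly outcomes follow. Nothing restricts the analysis to patients with CDI.

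**Eligible wards.** Section 5.5 admits medical, medical/surgical and surgical wards, the last described as "Adult Acute Surgical Ward: Hospital area for evaluation and treatment of patients who have undergone a surgical procedure". Patients need only be adults admitted to the unit; those admitted for bowel surgery are not excluded.

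**Randomisation.** Section 5.2.1 stratifies by location, with one intervention and one control unit per site. Ward type is not a stratification factor.

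**The concern.** These two outcomes presumably stand for severe consequences of CDI, which is the only reason for gloving to affect them. As defined, they are any coded colectomy or toxic megacolon. On a ward that receives patients after surgery, a colectomy can be why the patient is there, and gloving on that unit could not have caused or prevented it.

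Two harms could follow. Events unrelated to CDI pull the rate ratio towards 1 and hide a real effect. If ward types also differ between arms, surgical case mix can produce a difference that would be read as a benefit or harm of gloving on severe CDI.

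**Working it through.** The plan gives no figure for this outcome, so there is none to reproduce. The check compares definitions and then uses two illustrations on declared assumptions.

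**1. Neighbouring definitions in section 5.6**

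| Item | CDI link | Time limit |
|---|---|---|
| Patient-level CDI | is CDI itself | during admission |
| Patient-level CLABSI, CAUTI, MRSA | not applicable | during admission |
| Surgical history: "CDI-related surgical intervention prior to admission" | yes | before admission |
| Unit-level HO-CDI | is CDI itself | specimen more than 3 days after admission |
| Toxic megacolon, colectomy | none stated | none stated |

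The plan applies both kinds of limit elsewhere, but not here. The stated linkage does not supply them: it joins records and is not a condition for counting an event. The study cultures also measure "colonization, not infection" (section 5.6, Specimen collection).

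**2. Dilution**

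Let *f* be the share of control-arm events unrelated to CDI and unaffected by gloving, and RR the true rate ratio on CDI-related events. Then

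apparent RR = *f* + (1 − *f*) × RR.

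Take RR = 1 − 0.36 = 0.64, borrowing the 36% reduction that section 5.7.1 assumes for acquisition. Applying it to these outcomes is an assumption, and so is every value of *f*.

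| *f* | Calculation | Apparent RR |
|---|---|---|
| 0 | 0 + 1 × 0.64 | 0.64 |
| 0.50 | 0.50 + 0.50 × 0.64 | 0.82 |
| 0.80 | 0.80 + 0.20 × 0.64 | 0.93 |
| 0.90 | 0.90 + 0.10 × 0.64 | 0.96 |
| 0.95 | 0.95 + 0.05 × 0.64 | 0.98 |

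**3. Case mix with no true effect**

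Assume five equal-sized units per arm, one surgical unit in one arm and none in the other. Let *b* = 0.1% be the event rate on every non-surgical unit and *e* the rate on the surgical unit. Then

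between-arm ratio = [(*e* + 4*b*) / 5] / *b*.

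| *e* | Calculation | Ratio |
|---|---|---|
| 0.5% | (0.5 + 0.4) / 5 / 0.1 | 1.8 |
| 1% | (1 + 0.4) / 5 / 0.1 | 2.8 |
| 2% | (2 + 0.4) / 5 / 0.1 | 4.8 |
| 5% | (5 + 0.4) / 5 / 0.1 | 10.8 |

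Whether this looks like benefit or harm depends on which arm holds the surgical unit. If ward types match within each site, this mechanism largely disappears and dilution remains.

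**The case against.** The strongest reply is that the plan is incomplete here rather than wrong, and several parts of that reply stand.

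- A reader might infer that planned bowel surgery will be scored. The documents do not say so. The codes are only an example, no list is given, and the types of the ten units are not stated. The text permits such events; it does not show that any will be counted, or that a site's two units differ in type.
- A reader might infer that the events carry no dates. That goes too far. Monthly trends and analyses by period need dated events, and section 5.6 already extracts facility and unit admission and discharge dates. Recording earlier CDI-related surgery as history also suggests that outcomes were meant to fall after admission. What is missing is a stated window relative to unit admission and to CDI.
- Section 5.7.2 mentions covariate adjustment, and section 5.6 collects comorbidities such as cancer and inflammatory bowel disease. But no covariates are named and the chi-squared or Fisher comparison is unadjusted. Adjustment also cannot turn a colectomy done for another reason into a CDI outcome.
- Peak-infection wording appears in the paragraph on these outcomes, but it repeats the paragraph on other HAIs and proves little about intent.
- The surgical case-mix argument applies mainly to colectomy. Toxic megacolon is affected chiefly by the missing CDI link and window.

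A CDI-restricted outcome could probably be built from data largely planned already. The plan does not say that it will be.

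**Conclusion.** The point holds as a gap in the outcome rule. Sections 5.6 and 5.7.2 together compare all coded colectomy and toxic megacolon by arm, with no CDI condition and no window from unit admission. With surgical and medical/surgical wards eligible and stratification by site only, this can dilute a CDI effect or turn ward case mix into an apparent effect of gloving.

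Both directions follow from the definition; the size does not. The illustrations (apparent RR 0.82 to 0.98 instead of 0.64 for *f* from 50% to 95%; null ratios of 1.8 to 10.8) rest on assumed shares, rates, unit sizes and ward types. A reader might bring in outside colectomy and CDI rates and conclude that nearly all counted events would be unrelated to CDI. The documents supply none of those rates, so that conclusion is not available from them.

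Nor is it right to infer that the trial's main conclusions are at risk. These outcomes are not among the objectives in section 3.0. The point is minor, but worth correcting before analysis.

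**What to change.** In section 5.6 (Other clinical outcomes) and the matching paragraph of section 5.7.2:

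- Count only CDI-associated toxic megacolon or colectomy: an event dated after unit admission, in a patient whose CDI developed during the same admission and is dated on or before the event.
- Take CDI status from the patient-level CDI data already planned in section 5.6, with onset timing consistent with the unit-level HO-CDI definition there (specimen more than 3 days after admission). That paragraph counts from facility admission but also says that hospital means the study unit, so state which admission starts the clock. A rule accepting CDI from the first unit day would conflict with it.
- Give the code list.
- Report all-cause colectomy, if at all, separately and descriptively.

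**Cost.** Far fewer events will be counted, possibly too few for a useful test. CDI onset dates are needed. Patient-level CDI is planned from sources such as diagnostic codes, and clinical laboratory results are not a named patient-level item; they enter through the monthly unit aggregate. One laboratory-date field may therefore have to be added. Otherwise the change is a short edit in two places.
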